5.8 Patient Replacement

Patients who do not receive any dose of the study drug will be replaced.

6.0 STUDY PROCEDURES

6.1 SCHEDULE OF ASSESSMENTS:

	Screening (within 28 days)	C1D1	C2D1	C3D1	C4D1	D1C5+	EOT¹²	Follow Up⁸
Informed Consent	X							
Review Eligibility Criteria	X							
Demographics, Height	X							
Prior and Concomitant Medications	X	X	X	X	X	X	X	
Review Adverse Events¹⁰	X	X	X	X	X	X	X	
Physical Examination, Vital Signs¹, Weight	X	X	X	X	X	X	X	
ECOG Performance Status	X	X	X	X	X	X	X	
Survival Status								X Q3m
Laboratory Assessments								
Pregnancy Test for WOBCP²	X							
CBC with diff, platelets³	X	X	X	X	X	X	X	
Comprehensive Metabolic Panel, including Alk Phos⁴	X	X	X	X	X	X	X	

	Screening (within 28 days)	C1D1	C2D1	C3D1	C4D1	D1C5+	EOT ¹²	Follow Up ⁸
LDH	X	X	X	X	X			
PSA¹¹	X	X	X	X	X	X	X	X
Testosterone¹¹	X				X		X	
TSH, free T3, free T4 (If Clinically Indicated: FSH, LH, ACTH)	X	X	X	X	X	X ⁶	X	
Therapy								
Cohorts A and B Nivolumab 3 mg/kg IV q3 wks for up to 4 doses¹³				X				
Cohorts A and B Ipilimumab 1 mg/kg IV q3 wks for up to 4 doses¹³				X				
Cohorts A and B Nivolumab 480 mg IV q4 wks for up to 23 doses¹³						X		
Cohort C Nivolumab 480 mg IV q4 wks¹⁴				X		X		
Imaging Tumor Assessments								
CT chest	X					X (q 12 wks)		
CT Abdomen/Pelvis or MRI Abdomen/Pelvis⁵	X					X (q 12 wks)		
Tc^{99m} Bone Scan (prostate only)	X					X (q 12 wks)		
QoL: BPI-SF and EORTC QLQ C30	X					X (q 12 wks)		
Correlatives								
Tumor Tissue Archival (CRPC preferred if available)	X							
Tumor Biopsy	X						X ⁷	
Research blood⁹		X	X	X		X (q 12 wks)	X	

1. Vital signs will include temperature, pulse, respirations, blood pressure; height will be obtained at screening only.
2. WOCBP: Women of child bearing potential; urine or serum pregnancy test.
3. CBC with diff includes total WBC, hemoglobin, hematocrit and differential of the WBC including absolute counts.
4. COMP or Comprehensive metabolic profile includes sodium, potassium, chloride, bicarbonate, BUN, creatinine, AST, ALT, alkaline phosphatase, total bilirubin.
5. With or without intravenous contrast, before or on associated visit. CT or MRI (preferred) brain with or without IV contrast if suspected or known brain metastases. Frequency of tumor assessments will be q12 weeks.
6. Every 42 calendar days ± 14 business days. May be delayed if infusion is not scheduled within the window.
7. Optional tissue biopsy collection at progression if subject consents; +/- 14 working days.
8. Follow up with phone call or with clinic visit.
9. Blood for research should be collected prior to study treatment on C1D1, C2D1, C3D1 and C5D1, every 12 weeks thereafter and end of treatment.

10. Data on adverse events will be collected from the time of the initial study drug administration through 100 days after the last dose of study drug (nivolumab and/or ipilimumab) as described in Section 8.2.
11. For Cohort A only
12. End of Treatment Visit should occur within 3-4 weeks of last dose of protocol therapy.
13. Cohorts A and B (Nivolumab and Ipilimumab: 1 cycle (C) = 21 days (D) for up to 4 doses of Nivolumab (3mg/kg IV) and Ipilimumab (1mg/kg IV), then Nivolumab maintenance therapy alone (480mg IV): 1 cycle=4 weeks or 28 days (D). Total treatment time is up to 104 weeks.
14. Cohort C (Nivolumab monotherapy): 1 cycle (C) = 28 days (D) of Nivolumab monotherapy (480mg IV) for up to 104 weeks.

NOTE:

All procedures in study assessments schedule have a window of \pm 3 business days unless otherwise mentioned. Virtual clinic visits will be allowed per clinician/ subject discretion.

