7.0 MEASUREMENT OF EFFECT

7.1 Antitumor Effect- Prostate Cancer

While on therapy with either nivolumab alone or in combination with ipilimumab, patients with mCPRC will undergo laboratory monitoring on day 1 of each treatment cycle, including PSA, repeated every 4 weeks.

Evaluable for toxicity. All patients will be evaluable for toxicity from the time of their first treatment with study drug.

Evaluable for Objective PSA Response. All patients enrolled in Cohort A who received at least 1 cycle(s) of therapy, and who have 2 PSA measurements after protocol therapy initiation will be considered evaluable for PSA response. Patients who exhibit objective or clinical disease progression prior to collection of 2 PSA measurements will also be considered evaluable.

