7.1.1 PSA Response Rate

[figure not shown]
Per PCWG3 criteria, PSA response rate will be defined as the proportion of subjects who have PSA response as defined by at least 50% decline in PSA level from baseline measured twice at least 3 weeks apart. Based on the PCWG3 criteria, a favorable effect on PSA may be delayed for \geq 12 weeks. PSA will be monitored every 4 weeks, but treatment will be planned to continue through early rises for 12 weeks unless other evidence of progression, such as radiographic progression.

Therefore, early rises in PSA before 12 weeks will not be considered when determining PSA response.

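### The schedule's PSA footnote and the PSA-evaluability definition cover only Cohort A, although PSA response is also Cohort C's primary endpoint

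*Combined protocol and SAP*

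**What the plan says.** Two places limit PSA to Cohort A.

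- Section 6.1: superscript 11 sits on both the PSA row (screening, day 1 of every cycle, end of treatment, follow-up) and the testosterone row (screening, C4D1, end of treatment). The footnote reads "11. For Cohort A only".
- Section 7.1: the evaluable set for PSA response is "All patients enrolled in Cohort A who received at least 1 cycle(s) of therapy, and who have 2 PSA measurements after protocol therapy initiation". A second sentence adds: "Patients who exhibit objective or clinical disease progression prior to collection of 2 PSA measurements will also be considered evaluable".

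Several other places require PSA in Cohort C or depend on it.

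- The opening of 7.1 says: "While on therapy with either nivolumab alone or in combination with ipilimumab, patients with mCPRC will undergo laboratory monitoring", with PSA among the day-1 tests. Nivolumab alone from the start is the Cohort C regimen.
- Section 7.1.1 says "PSA will be monitored every 4 weeks", with no cohort limit, and defines response as "at least 50% decline in PSA level from baseline measured twice at least 3 weeks apart".
- Section 11.1 gives Cohort C its own PSA decision rule, 11.2 plans 50 PSA-evaluable prostate patients, and 11.3 names PSA response as the primary endpoint of both prostate cohorts.
- Sections 3.1.5 and 3.1.6 set screening PSA and testosterone requirements for every subject with prostate cancer.

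**The concern.** Sites work from the schedule of assessments. For Cohort C it says not to draw the marker on which the cohort's primary endpoint rests, while the body text says to draw it. The analysis set has the same conflict: section 11 needs a PSA-evaluable Cohort C population, and the one definition offered does not include it.

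At stake are PSA values that cannot be obtained afterwards, and a primary-endpoint denominator that might be settled only once responses are known. Cohort C supplies half of the planned primary-endpoint patients.

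**Working it through.** **1. The plan's own design figure.** Inputs from 11.1 for Cohort C: n = 25, success at 6 or more PSA responses, reference rate 10%, target rate 30%, one-sided type I error 5%, power 80%. With P(X ≥ 6) = Σ C(25, x) pˣ (1 − p)²⁵⁻ˣ over x = 6 to 25:

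- p = 0.10 gives 0.0334, within the 5% limit.
- p = 0.30 gives 0.8065, matching the stated 80%.

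The arithmetic of the design is sound. The problem lies in who is measured and who is counted.

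**2. The evaluable count.** Section 11.2 needs 50 PSA-evaluable prostate patients. Section 11.1 takes 25 evaluable from Cohort A, so 50 − 25 = 25 must come from Cohort C. The first sentence of the 7.1 definition admits only Cohort A, so it covers 25 of the 50. The second sentence does not repeat the cohort limit. Read literally on its own, it would make early progressors the only evaluable Cohort C patients, which 11.2 shows is not intended.

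**3. Is the limit deliberate?** The same schedule has a Cohort C dosing row with its own footnote 14, and it labels another row "Bone Scan (prostate only", which includes Cohort C. No section gives a reason to exempt Cohort C from PSA.

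**4. Which PSA values have another source?** Per Cohort C patient, using the 26 doses in 5.1.1 and the follow-up in 5.6:

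| PSA value | Maximum number | Source outside the restricted row |
|---|---|---|
| Screening | 1 | 3.1.5 |
| Day 1 of each cycle | 104 / 4 = 26 | opening of 7.1 |
| End of treatment | 1 | 7.1.1, if four-weekly monitoring is read to run past the last dose |
| Follow-up | 24 / 3 = 8 | none |
| Total | 36 | 27 clear, 1 arguable, up to 8 none |

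The dosing table in 5.1 gives 23 doses in the row that includes Cohort C. That count gives 1 + 23 + 1 + 8 = 33 values: 24 clear, 1 arguable and up to 8 with none. The two dose counts need reconciling; the conclusion here is the same under either. Eight follow-up values is a ceiling, because the follow-up cell is a bare X and footnote 8 reads "8. Follow up with phone call or with clinic visit".

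For testosterone the row holds 3 values. Screening is covered by 3.1.6; C4D1 and end of treatment appear only in the restricted row.

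**5. When the end-of-treatment value decides a patient's status.** Footnote 12 places that visit 3 to 4 weeks after the last dose.

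- Response needs two qualifying values at least 3 weeks apart. If the decline first appears at the last dosing visit, the end-of-treatment PSA is the next scheduled value.
- Assume day-1 PSA is drawn before the dose. A non-progressing Cohort C patient who stops after exactly two doses then has one on-treatment post-initiation value, at C2D1. The end-of-treatment value would be the second one that evaluability requires.

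Follow-up PSA is counted here only toward secondary endpoints (PSA progression and duration of response).

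**6. The denominator.** Section 11.1 enrols Cohort A until 25 are evaluable but says only that Cohort C accrues 25 patients. Section 5.8 replaces only patients who were never dosed. Suppose some dosed Cohort C patients have no usable PSA, are not replaced and cannot count as responders. With the cut-off held at 6 and a true rate of 30%, power by number of usable patients is:

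| Usable patients | 25 | 24 | 23 | 20 |
|---|---|---|---|---|
| Power | 0.807 | 0.771 | 0.731 | 0.584 |

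This shows sensitivity only. The documents give no loss rate.

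**The case against.** The strongest reply is that the documents largely resolve the conflict themselves. The body text requires day-1 PSA for patients on nivolumab alone, 3.1.5 requires a screening value, and section 11 leaves no doubt that Cohort C is judged on PSA. The end-of-treatment visit falls at about the time the next four-weekly PSA would be due, and both cases in which it decides a patient's status are narrow. Follow-up PSA is not guaranteed in Cohort A either, since contact may be by phone. The Cohort C denominator follows from the 50 in 11.2. No bias or loss of power has been measured, and the remedy adds tests that the primary response count does not need.

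Most of this stands as a limit on the size of the problem. On-treatment PSA would probably be drawn, the intended denominator can be inferred, and no affected count can be given. It does not remove the contradiction. A reader must override both an explicit footnote and the only evaluability definition to reach the intended plan. End-of-treatment PSA still rests on an arguable reading, and replacement of dosed but non-evaluable Cohort C patients is not stated.

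**Conclusion.** The concern holds and must be fixed. As written, footnote 11 and the 7.1 definition leave Cohort C without scheduled PSA and without a stated evaluable set for its primary endpoint. That contradicts the opening of 7.1 and sections 11.1 to 11.3.

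Three points remain unsettled: end-of-treatment PSA, follow-up PSA, and the Cohort C denominator. The first and third can touch the primary result. The statement about two-dose patients assumes pre-dose day-1 sampling. The value counts are maxima under full treatment and follow-up. The design figures are correct and are not in dispute.

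**What to change.** One short amendment with four wording changes:

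1. Footnote 11 in 6.1: apply it to Cohorts A and C (mCRPC).
2. Section 7.1, definition of PSA evaluability: name Cohorts A and C.
3. Section 11.1: state that Cohort C accrues 25 PSA-evaluable patients, matching the 50 in 11.2.
4. Section 11.3, as clean-up: extend the sentence on PSA progression-free survival and time to PSA progression from Cohort A to Cohorts A and C. Section 2.5.3 already sets these endpoints for all mCRPC subjects. Keep the existing reporting overall, where applicable, and by cohort.

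Sample size, cut-off, type I error and power stay as they are. Screening and day-1 PSA are already required by 3.1.5 and 7.1, and end-of-treatment PSA becomes explicit. The added burden is 2 testosterone tests per Cohort C patient, at most 2 × 25 = 50, at visits where blood is already drawn. PSA is also added at follow-up contacts held in clinic, at most 8 per patient. If the sponsor wants testosterone to stay limited to Cohort A, the PSA row can be given its own footnote.

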7.0 MEASUREMENT OF EFFECT

7.1 Antitumor Effect- Prostate Cancer

While on therapy with either nivolumab alone or in combination with ipilimumab, patients with mCPRC will undergo laboratory monitoring on day 1 of each treatment cycle, including PSA, repeated every 4 weeks.

Evaluable for toxicity. All patients will be evaluable for toxicity from the time of their first treatment with study drug.

Evaluable for Objective PSA Response. All patients enrolled in Cohort A who received at least 1 cycle(s) of therapy, and who have 2 PSA measurements after protocol therapy initiation will be considered evaluable for PSA response. Patients who exhibit objective or clinical disease progression prior to collection of 2 PSA measurements will also be considered evaluable.

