5.4 Duration of Therapy

In the absence of treatment delays due to adverse events, treatment may continue for a total of 104 weeks in all from the start of study therapy or until one of the following criteria apply:

- Disease progression as defined in Section 7.0
- Inter-current illness that prevents further administration of treatment
- Unacceptable adverse event(s)
- Patient voluntarily withdraws from treatment
- General or specific changes in the patient's condition render the patient unacceptable for further treatment in the judgment of the investigator

Do not hold scans, continue scan schedule every 12 weeks from cycle 5 day 1 regardless of treatment delays thereafter.

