7.2.1 Definitions

Evaluable for toxicity. All patients will be evaluable for toxicity from the time of their first treatment with study drug.

Evaluable for objective response. All patients enrolled who received at least 1 cycle(s) of therapy, and who have measurable disease present at baseline and have had their disease re-evaluated will be considered evaluable for response. These patients will have their response classified according to the definitions stated below. (Note: Patients who exhibit objective or clinical disease progression prior to the end of cycle 1 will also be considered evaluable.)

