7.4.3 Evaluation of Best Overall Response

The best overall response is the best response recorded from the start of the treatment until disease progression/recurrence (taking as reference for progressive disease the smallest measurements recorded since the treatment started). The patient's best response assignment will depend on the achievement of both measurement and confirmation criteria.

Evaluation as per RECISTv1.1 and irRECIST.

Target Lesions	Non-Target Lesions	New Lesions	Overall Response per RECIST 1.1	Overall Response per irRECIST (Cohort B only)	Best Response for this Category Also Requires:
CR	CR	No	CR	N/A	>4 wks. confirmation
CR	CR Non-CR/SD	No	PR	N/A	>4 wks. confirmation
PR	CR Non-CR/PD	No			
SD	CR Non-CR/PD	No	SD	N/A	documented at least once >4 wks. from baseline
PD	Any	Any	PD	irSD	>4 wks. from baseline;
Any	PD*	Any			
Any	Any	Yes			
PD	Any	Any	N/A	irPD	No further confirmation required
Any	PD*	Any			
Any	Any	Yes			

*In exceptional circumstances, unequivocal progression in non-target lesions may be accepted as disease progression.

Note: Patients with a global deterioration of health status requiring discontinuation of treatment without objective evidence of disease progression at that time should be reported as "*symptomatic deterioration*." Every effort should be made to document the objective progression even after discontinuation of treatment.

N/A=not applicable

Note: If subjects respond to treatment and are able to have their disease resected, the patient's response will be assessed prior to the surgery

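### Response appears to be counted among patients made evaluable by post-dose events, with no all-treated response rate planned; Cohort B's early-failure exception stops at week 3, but its first scheduled scan is at about week 12

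*Combined protocol and SAP*

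**What the plan says.** **Cohort A (primary endpoint).** Under section 7.1, Cohort A patients with at least one cycle and "who have 2 PSA measurements after protocol therapy initiation will be considered evaluable for PSA response". The same section keeps early failures in: "Patients who exhibit objective or clinical disease progression prior to collection of 2 PSA measurements will also be considered evaluable". Section 7.1.1 requires the PSA decline to be seen twice, at least 3 weeks apart.

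**Cohort B (secondary endpoint).** Under section 7.2.1, patients with at least one cycle and "who have measurable disease present at baseline and have had their disease re-evaluated will be considered evaluable for response". The exception is shorter than Cohort A's: "Patients who exhibit objective or clinical disease progression prior to the end of cycle 1 will also be considered evaluable". Section 5.4 tells sites to "continue scan schedule every 12 weeks from cycle 5 day 1 regardless of treatment delays thereafter", and section 6.1, footnote 5, says "Frequency of tumor assessments will be q12 weeks". The 6.1 table shows imaging at screening and from cycle 5 day 1, with none at end of treatment or follow-up. Section 7.4.3 gives a separate label to patients with "global deterioration of health status requiring discontinuation of treatment without objective evidence of disease progression" and adds: "Every effort should be made to document the objective progression even after discontinuation of treatment". It does not make them evaluable.

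**Cohort C (primary endpoint).** No evaluability rule is written. Section 7.1 names Cohort A only, footnote 11 to the schedule restricts the PSA row to Cohort A, and 11.1 plans 25 mCRPC patients without the evaluable qualifier.

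**Counts and analysis.** Section 11.1 runs Cohort A to 25 evaluable patients with an interim after 15 evaluable. Section 11.2 totals 50 PSA-evaluable and 15 response-evaluable patients. The synopsis gives 25 and 15 for Cohort A without that qualifier. Section 11.3 plans counts, proportions and exact intervals and names no denominator. An all-dosed set is defined only for safety (7.7). Section 5.8 replaces only undosed patients.

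**The concern.** Evaluability is decided by what happens after dosing, and the patients it removes are not a random subset. Someone with no re-evaluation (Cohort B), or without two post-baseline PSA values (Cohort A), cannot be a documented responder. Removing such patients from the denominator can only raise the response rate. Accruing to a fixed evaluable count then in effect replaces them, which section 5.8 does not provide for.

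The gap is clearest in Cohort B, because the exception and the scan schedule do not meet: about nine weeks lie between them. With 15 patients and a rule of 3 responses, each excluded patient moves the estimate by about a percentage point, and nothing in 11.3 would show the reader that it had happened.

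**Working it through.** **1. Reproduce the plan's figures (section 11.1).** Exact binomial, X ~ Bin(n, p).
- Cohort A, minimax Simon: continue if at least 2 of 15, succeed if at least 6 of 25. P(success) = sum over x >= 2 of P(X1 = x; 15, p) × P(X2 >= 6 - x; 10, p). At p = 0.10: 0.0328. At p = 0.30: 0.802 (stated 80%).
- Cohort C: P(X >= 6; 25, p). At 0.10: 0.0334. At 0.30: 0.807 (stated 80%).
- Cohort B: P(X >= 3; 15, p). At 0.05: 1 - (0.4633 + 0.3658 + 0.1348) = 0.0362. At 0.25: 1 - (0.0134 + 0.0668 + 0.1559) = 0.764 (stated 76%).

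The stated figures reproduce. The issue is who is in n.

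**2. The Cohort B window.** An induction cycle is 21 days (6.1, footnote 13). The exception therefore ends at week 3. Cycle 5 day 1 falls after 4 × 3 = 12 weeks. A patient who fails clinically, dies or stops in weeks 3-12 meets neither the rule nor the exception unless disease is re-evaluated. A patient scanned off schedule has been re-evaluated and stays in.

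**3. The Cohort A window.** Progressors before two PSAs are kept, and PSA is drawn each cycle, at end of treatment and in follow-up. What remains is mainly withdrawal, a toxicity stop or death without documented progression before two PSAs.

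**4. Shift in the reported rate.** Let q be the probability that a dosed patient is excluded for lack of the required assessment. Such patients have no documented response, so evaluable rate = all-treated rate / (1 - q). At results that just pass:

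| Excluded | Evaluable | All treated |
|---|---|---|
| 1 | 6/25 = 24.0% | 6/26 = 23.1% |
| 3 | 6/25 = 24.0% | 6/28 = 21.4% |
| 1 | 3/15 = 20.0% | 3/16 = 18.8% |
| 3 | 3/15 = 20.0% | 3/18 = 16.7% |

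The exact 95% intervals are 9.4-45.1% for 6/25 and 4.3-48.1% for 3/15.

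**5. Type I error, only if the 10% and 5% references are all-treated rates.** Put p = p0/(1 - q) into step 1. The documents give no q, so these values are assumed.

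| q | A | C | B |
|---|---|---|---|
| 0 | 3.3% | 3.3% | 3.6% |
| 2% | 3.6% | 3.6% | 3.8% |
| 5% | 4.1% | 4.2% | 4.1% |
| 10% | 5.1% | 5.2% | 4.7% |

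The 5% line is crossed at q of about 9.5% (A), 9.1% (C) and 12.0% (B). If the references are evaluable-patient rates, the q = 0 row applies throughout.

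**6. Power if the go rules moved to all dosed patients at unchanged n**, with the 30% and 25% targets meant for evaluable patients. Put p = p1(1 - q) into step 1.

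| q | A | C | B |
|---|---|---|---|
| 0 | 80% | 81% | 76% |
| 5% | 75% | 76% | 73% |
| 10% | 70% | 70% | 69% |

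**The case against.** The sponsor has fair answers, and several stronger readings that a reader might infer do not stand.

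- **That the plan states an evaluable-only denominator.** It does not. Section 7.1.1 speaks of the proportion of subjects, 11.3 of the mCRPC cohort, and the synopsis of patients. The evaluable denominator is an inference from 7.1, 7.2.1 and 11.1-11.2. It is the natural reading, but the silence of 11.3 supports clarifying the text rather than a claim that a wrong set was chosen.
- **That Cohort B drops everyone who fails between week 3 and the first scan.** It does not. Re-evaluation is not tied to a scheduled scan, and 7.4.3 asks sites to pursue objective progression after treatment stops. Only patients with no re-evaluation at all are lost.
- **That the primary endpoint is seriously biased.** The Cohort A exception removes most of the problem there.
- **That type I error exceeds 5%.** This needs all-treated references and an exclusion share above about 9-12%. The documents support neither. Section 11.1 attaches the power to evaluable patients, which if anything points the other way.
- **That the shift is large.** One lost patient moves the rate by about one percentage point, small beside the intervals above.

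The 1/(1 - q) relation also does not cover local-intervention patients, whom 5.3 allows to be called not evaluable. They may respond, so the direction of bias is uncertain.

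What stands: in Cohort B the exception and the scan schedule do not meet, Cohort C has no rule, and no all-treated response rate is planned.

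**Conclusion.** The point holds in this limited form. Followed as written, the plan excludes some dosed patients who cannot be documented responders, mainly in Cohort B, and so raises the reported response rate. The direction is certain for patients lacking the required assessment; the size depends on q, which the documents do not give. One excluded patient is worth 0.9 percentage points at 6/25 (24.0 - 23.1) and about 1.2 at 3/15 (20.0 - 18.75).

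The conclusion rests on two readings: that the denominator left open in 11.3 is the evaluable set, and that re-evaluated in 7.2.1 means some actual disease assessment. It does not rest on any error in the design arithmetic, which is right, and it does not establish a breach of the 5% level. It is worth correcting because the remedy is cheap and the exclusions would otherwise be invisible.

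**What to change.** - **7.2.1:** count Cohort B patients who received a dose and then progress clinically, die or stop treatment before the first post-baseline assessment, with none obtained later, as evaluable non-responders. State what counts as re-evaluation.
- **7.1:** do the same for Cohort A patients who stop or die without two post-baseline PSAs. Extend the definition to Cohort C, and align footnote 11 of 6.1 with it.
- **11.3:** name the response denominator. Add for each cohort an all-treated response rate with exact interval, counting no documented response as non-response, beside the evaluable rate, with the number of and reason for each exclusion.
- **Synopsis, 5.8 and 11.1-11.3:** use one description of the counted patients, and say how dosed non-evaluable patients are handled in accrual.
- **Design:** keep n and the 2/15, 6/25 and 3/15 cut-offs, applied to the widened evaluable set. Label the change as post hoc for any cohort whose data have been seen.

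**Cost.** Wording, a slightly lower reported rate and, if q is not zero and the targets were evaluable-based, some power. The widened set moves towards all dosed patients, so the last table in the working bounds the loss: at q = 5%, no lower than about 75/76/73% (A/C/B). Moving the go rules formally to all dosed patients is optional. At unchanged n it would incur that full loss, which is a trade-off for the sponsor to decide, not a correction.
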